## APPENDIX C: DEMOGRAPHICS SURVEY (CHILD)

### Demographics (child)

This survey is about the children in your household. You will be asked to repeat the survey for each child. Please answer all the questions for each child.

Thank you!

#### For the Interviewer

##### New Study ID for the Child

This is the adult person's study ID number with site variable added (No Action Needed - Please Note on Specimen Log Sheets)

---

Child Number

(Please indicate with 2 numbers. For example, the first or oldest child in the household would be 01, next child would be 02, next 03, etc.)

---

This is the child's study ID. Please add the child number to the end of the Adult Study ID (e.g., "child number": 01, "adult study ID": 210, "child study ID": 21001)

---

Today's Date

---

## APPENDIX D: STRUCTURED VISIT FORM

### Structured Visit Form (CHW)

Page 1

Please complete this form after you have completed the home visit.

Thank you!

#### Home Visit Log

Today's date

Name of Community Health Worker

- [name]
- [name]
- [name]

Home visit number

- Home visit 1 - health education (SV 2)
- Home visit 2 - health education (SV 3)
- Home visit 3 - self efficacy (SV 5)
- Home visit 4 - self efficacy (SV 6)
- Home visit 5 - self efficacy (SV 7)
- Home visit 6 - check in (SV 9)
- Home visit 7 - check in (SV 10)
- Home visit 8 - check in (SV 11)
- Home visit 9 - check in (SV 12)

What time did you arrive at the home?

What time did you leave the home?

Page 2

#### Checklist for each study visit (completed by the Community Health Worker)

	Yes	No	Not applicable
Caregiver was available to make a study appointment			
Caregiver was ready for study appointment at the agreed upon date and time			
Study appointment had to be rescheduled by the caregiver			
(All) enrolled child(ren) present			
Caregiver completed assignment ahead of time			
Home was too loud during visit			
Caregiver appeared distracted (using cell phone, cooking, other)			
Was able to complete all study visit tasks			

Number of scheduling attempts made before study visit took place

Other problems

Field notes from visit

Any other notes

## APPENDIX E: FRUIT DRINK SURVEY

(Please read to caregiver)

We are going to be talking about sugared fruit drinks: the kinds of drinks where you add a powdered mix to water. We will use Tang and Kool-Aid as examples of sugared fruit drinks, which could also include drinks like Hawaiian Punch and Country Time Lemonade. Keep in mind that we are not talking about soda pop or the warm Tang you give to your child when he/she is sick. For each statement, please choose whether you strongly agree, agree, have no opinion, disagree, or strongly disagree.

### Section 1

	Strongly agree	Agree	No opinion	Disagree	Strongly disagree
Tang and Kool-Aid are healthy for my child. [in general]					
It is important to limit how much Tang and Kool-Aid my child drinks.					
Watering down Tang and Kool-Aid makes them healthier. [adding more water than the package says so it's diluted]					
Preventing cavities is important.					
It is important for me to help my child to be cavity-free.					
Sugar-free drinks are unsafe					

[Present photo of sugar-free Tang and Kool-Aid to participants and say]: Here is a picture of sugar-free Tang and Kool-Aid.

Have you seen these drinks before?

Yes  
 No

**Here are some more statements regarding sugar-free Tang and Kool-Aid. Please answer whether you strongly agree, agree, have no opinion, disagree, or strongly disagree.**

**Section 1A**

	Strongly Agree	Agree	No opinion	Disagree	Strongly Disagree
Sugar-free Tang and Kool-Aid are healthier than regular Tang and Kool-Aid.					
Sugar-free Tang and Kool-Aid are not as tasty as regular Tang and Kool-Aid.					

**The following statements are related to supervising/controlling your child's drink intake. For the following statements, please choose whether you strongly agree, agree, have no opinion, disagree, or strongly disagree.**

**Section 2**

	Strongly agree	Agree	No opinion	Disagree	Strongly disagree
I can get my child to drink less regular Tang and Kool-Aid					
I can get my child to drink sugar-free Tang and Kool-Aid					

**The following statements are related to products you see in the store. For the following, please answer whether the statements are often, sometimes, or never true.**

**Section 3**

	Often	Sometimes	Never
Sugar-free Tang and Kool-Aid are available in my village			
Crystal Light is available in my village			
Other adults in my home, like grandparents or relatives, give my child regular Tang and Kool-Aid			

**The following statements are about Tang and Kool-Aid. For the following statements, please choose whether you believe each statement is true or false.**

**Section 4**

	True	False
Tang and Kool-Aid contain vitamin C		
Tang and Kool-Aid are healthier than soda pop		
Sugar-free Tang and Kool-Aid lead to cavities in children		

As a reminder, sugared fruit drinks include Tang, Kool-Aid, Hawaiian Punch, Country Time Lemonade, and other kinds of drinks where you add a powdered mix to water. Do you give your child sugared fruit drinks?

Yes  
 No

**(Staff - Please skip this section if the parent says no to the previous question. No questions will appear if they said no.)**

**Below are some reasons parents give their child sugared fruit drinks. Please tell me which apply to you. You can answer with a "Yes" or "No". You can answer yes to as many as you think apply to you.**

**(Staff - Please repeat the phrase "Parents give their child sugared fruit drinks..." before each statement)**

**Section 5**

	Yes	No
Because they are a good replacement for fruits, like oranges and grapes		
Because they are a good treat for my child		
Because they are inexpensive or cheap		
Because they make my child happy		
Because others in my village drink them		
Because they are healthier than soda pop		
Because there are few other drinks that I can give my kids		
Because they are what I grew up with		
Because they are part of being a child		

What are some other reasons you give your child regular Tang and Kool-Aid?

As a reminder, examples of sugar-free fruit drinks are Crystal Light, sugar-free Tang, and sugar-free Kool-Aid. Do you give your child sugar-free drinks?

Yes  
 No

**(Staff - Please skip this section if the parent says no to the previous question. No questions will appear if they said no.)**

**Below are some reasons parents give their child sugar-free fruit drinks. Please tell me which apply to you. You can answer with a "Yes" or "No". You can answer yes to as many as you think apply to you.**

**(Staff - Please repeat the phrase "Parents give their child sugar-free fruit drinks... before each statement.)**

**Section 6**

	Yes	No
Because they are a good replacement for fruits like oranges and grapes		
Because they are a good treat for my child		
Because they are inexpensive or cheap		
Because they make my child happy		
Because others in my village drink them		
Because they are healthier than soda pop		
Because they are part of being a child		

What are some other reasons you give your child sugar-free drinks?

---

## APPENDIX F: PAPER VERSION OF FRUIT DRINK SURVEY

REDUCING SUGARED FRUIT DRINKS IN ALASKA NATIVE CHILDREN  
FRUIT DRINK SURVEY  
SEPTEMBER 2023  
[«SURVEY\_»][«MATCH\_ID»]

*This section is to be completed by UW Study staff.*

DATE: \_\_\_\_ / \_\_\_\_ / \_\_\_\_ TIME: \_\_\_\_\_ COMMUNITY: «COMMUNITY»

Household ID: «HOUSEHOLD\_ID» Caregiver ID: \_\_\_\_\_ Child ID: «CHILD\_ID» Combined ID: \_\_\_\_\_

Please answer the questions on this form for this child [CHILD NAME: «FULL\_NAME»]

What is your relationship to this child [«FIRST\_NAME»]?

*Please circle one.*

Mother	Father	Grandmother	Grandfather	Aunt	Uncle	Other
--------	--------	-------------	-------------	------	-------	-------

These questions are about sugared fruit drinks. The kind where you add a powdered mix to water like Tang and Kool-Aid.

Keep in mind that we are not asking about soda-pop or the warm tang you may give your child when he/she is sick.

*For each of the following, please circle one response.*

Tang and Kool-Aid are healthy for my children, in general.	Strongly Agree	Agree	No Opinion	Disagree	Strongly Disagree
It is important to limit how much Tang and Kool-Aid my children drink.	Strongly Agree	Agree	No Opinion	Disagree	Strongly Disagree
Preventing cavities is important.	Strongly Agree	Agree	No Opinion	Disagree	Strongly Disagree
It is important for me to help my children to be cavity-free.	Strongly Agree	Agree	No Opinion	Disagree	Strongly Disagree
Sugar-free drinks are unsafe.	Strongly Agree	Agree	No Opinion	Disagree	Strongly Disagree

Quvana for your responses!

Page 1 of 4

REDUCING SUGARED FRUIT DRINKS IN ALASKA NATIVE CHILDREN  
FRUIT DRINK SURVEY  
SEPTEMBER 2023  
[«SURVEY\_»][«MATCH\_ID»]

Have you seen these drinks before?		Please circle one.
Tang and Kool-Aid  	Sugar-free Tang and Kool-Aid  	YES
		NO

These statements are about supervising/controlling your child's drink intake .					
For each of the following, please circle one response.					
I can get [«FIRST_NAME»] to drink less regular Tang and Kool-Aid.	Strongly Agree	Agree	No Opinion	Disagree	Strongly Disagree
I can get [«FIRST_NAME»] to drink sugar-free Tang and Kool-Aid.	Strongly Agree	Agree	No Opinion	Disagree	Strongly Disagree

Quvana for your responses!

Page 2 of 4

REDUCING SUGARED FRUIT DRINKS IN ALASKA NATIVE CHILDREN  
FRUIT DRINK SURVEY  
SEPTEMBER 2023  
[«SURVEY\_»][«MATCH\_ID»]

The following statements are related to products you see in the store.			
For each of the following, please circle one response.			
Sugar-free Tang and Kool-Aid are available in my village.	Often	Sometimes	Never
Crystal Light is available in my village.	Often	Sometimes	Never
Other adults in my home, like grandparents or relatives, give my child regular Tang and Kool-Aid.	Often	Sometimes	Never

The following statements are about Tang and Kool-Aid.		
For each of the following, please circle one response.		
Tang and Kool-Aid contain vitamin C.	True	False
Tang and Kool-Aid are healthier than soda pop.	True	False
Sugar-free Tang and Kool-Aid lead to cavities in children.	True	False

As a reminder, sugared fruit drinks include Tang, Kool-Aid, Hawaiian Punch, Country Time Lemonade, and other kinds of drinks where you add a powdered mix to water.		
Please circle one response.		
Do you give [«FIRST_NAME»] sugared fruit drinks?	Yes	No

Quyana for your responses!

Page 3 of 4

REDUCING SUGARED FRUIT DRINKS IN ALASKA NATIVE CHILDREN  
FRUIT DRINK SURVEY  
SEPTEMBER 2023  
[«SURVEY\_»][«MATCH\_ID»]

Below are some reasons parents give their child sugared fruit drinks.		
For each of the following, please circle one response if it applies to you and [«FIRST_NAME»].		
	Yes	No
Parents give their child sugared fruit drinks because they are a good replacement for fruits, like oranges and grapes.	Yes	No
Parents give their child sugared fruit drinks because they are a good treat for my child.	Yes	No
Parents give their child sugared fruit drinks because they are inexpensive or cheap.	Yes	No
Parents give their child sugared fruit drinks because they make my child happy.	Yes	No
Parents give their child sugared fruit drinks because others in my village drink them.	Yes	No
Parents give their child sugared fruit drinks because they are healthier than soda pop.	Yes	No
Parents give their child sugared fruit drinks because there are few other drinks that I can give my kids.	Yes	No
Parents give their child sugared fruit drinks because they are what I grew up with.	Yes	No
What are some other reasons you give [«FIRST_NAME»] regular Tang and Kool-Aid?		
Please write your response below.		

Page 4 of 4

## APPENDIX G: FOOD SURVEY

### Please read the following questions to the Caregiver

How often does your money for food run out before the end of the month?

- Never
- Seldom
- Sometimes
- Most times
- Always

In the past 12 months, the food you bought just didn't last, and you didn't have money to get more. Is this statement always, sometimes, or never true?

- Always True
- Sometimes True
- Never True

In the past 12 months, you worried whether your food would run out before you got money to buy more. Is this statement always, sometimes, or never true?

- Always True
- Sometimes True
- Never True

Do you receive assistance to pay for food (i.e., food stamps or WIC coupons)?

- Yes
- No

How much of your child's home diet consists of eating traditional Alaska Native foods?

- A lot
- Sometimes
- Rarely
- Not at all

How much does your household eat traditional Alaska Native foods?

- A lot
- Sometimes
- Rarely
- Not at all

Please specify how much traditional Alaska Native food each child consumes.

What percentage of your first child's home-based caloric intake consists of Alaska Native foods?  
(0%-100%)

What percentage of your second child's home-based caloric intake consists of Alaska Native foods?  
(0%-100%)

What percentage of your third child's home-based caloric intake consists of Alaska Native foods?  
(0%-100%)

What percentage of your fourth child's home-based caloric intake consists of Alaska Native foods?  
(0%-100%)

What percentage of your fifth child's home-based caloric intake consists of Alaska Native foods?  
(0%-100%)

What percentage of your sixth child's home-based caloric intake consists of Alaska Native foods?  
(0%-100%)

---

What percentage of your seventh child's home-based caloric intake consists of Alaska Native foods? (0%-100%) \_\_\_\_\_

---

What percentage of your eighth child's home-based caloric intake consists of Alaska Native foods? (0%-100%) \_\_\_\_\_

---

What percentage of your ninth child's home-based caloric intake consists of Alaska Native foods? (0%-100%) \_\_\_\_\_

---

What percentage of your tenth child's home-based caloric intake consists of Alaska Native foods? (0%-100%) \_\_\_\_\_

---

Are you currently breastfeeding or feeding pumped milk to a new baby?

Yes  
 No  
 Not applicable

---

Does your child spend most of their time living with you (more than half the time)?

Yes  
 No

## APPENDIX H: HAIR SURVEY (CAREGIVER)

### Hair Survey (caregiver)

Page 1

Please complete all the information about the caregiver.

#### For staff use only

Today's Date

---

Name of staff collecting hair sample

- [name]
- [name]
- [name]
- [name]
- [name]

Hair type

- Long
- Short

#### Please read the following questions to the Caregiver

Is your hair currently colored?

- Yes
- No

Is all of your hair colored or just sections?

- All
- Just Sections

Which type of hair coloring products did you use?

- Bleach
- Permanent hair dye
- Semi-permanent or temporary hair dye
- Wash out hair dye

## APPENDIX I: HAIR SURVEY (CHILD)

### Hair Survey (child)

Page 1

Please complete for each child.

#### For staff use only

Today's Date

---

Name of staff collecting hair sample

- [name]
- [name]
- [name]
- [name]
- [name]

Child's Study ID Number

---

Hair type

- Long
- Short

Weight (lbs)

---

#### Please read the following questions for the Caregiver

Is your child's hair currently colored?

- Yes
- No

Is all of your child's hair colored or just sections?

- All
- Just sections

Which hair coloring products were used by your child?

- Bleach
- Permanent hair dye
- Semi-permanent or temporary hair dye
- Wash-out hair dye

## APPENDIX J: SIDE EFFECTS AND ADVERSE EVENTS FORM

Page 1

### Side Effects and Adverse Events

Please answer the following questions about any adverse effects you may have experienced.

#### For the Interviewer

Today's date

---

Was this a home visit or a clinic visit?

Home visit  
 Clinic visit

---

What home visit number was this?

Home visit 1 - health education (SV 2)  
 Home visit 2 - health education (SV 3)  
 Home visit 3 - self efficacy (SV 5)  
 Home visit 4 - self efficacy (SV 6)  
 Home visit 5 - self efficacy (SV 7)  
 Home visit 6 - check in (SV 9)  
 Home visit 7 - check in (SV 10)  
 Home visit 8 - check in (SV 11)  
 Home visit 9 - check in (SV 12)

**(Please read to caregiver)**

**The following questions are regarding any adverse incidents that may have happened since the last time we visited. Please answer any or all questions that you and your children experienced.**

Since the last time we visited, has your child or anyone in your family had or currently have an upset stomach, runny stool, or diarrhea?

Yes  
 No

Which of the following did your child have? Select all that apply.

Upset Stomach  
 Runny Stool  
 Diarrhea  
 Other

Please specify what type of side effect your child experienced.

How bad was the side effect(s)?

Mild  
 Moderate  
 Severe

What do you think the reason was for this side effect?

What made it better?

Do you think this was related to the sugar-free fruit drinks?

Yes  
 No

Who mixed the sugar-free drinks?

Did the person who mixed the sugar-free drinks follow the study instructions?

Yes  
 No  
 I don't know

Was the container of sugar-free mix stored out of reach of children?

Yes  
 No  
 I don't know

Did an adult supervise your child's intake of the sugar-free drink?

Yes  
 No  
 I don't know

Did the child get more sugar-free drink than the card recommends?

Yes  
 No  
 I don't know

How much more than the card recommendation did your child drink?

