## ASSESSMENT OF SAFETY

### 8.1 Specification of Safety Parameters

Safety concerns include potential side effects associated with excess intake of the artificial sweeteners in the sugar-free water enhancers (sucratose and ace-K). Side effects include gastrointestinal effects, stomachache, and diarrhea. Additional side effects may include allergic reactions, changes in insulin sensitivity, alterations in gastrointestinal microbiota, weight gain, and decreased satiety. Precautions will be taken as part of the intervention to educate caregivers on how to minimize intake of the target sugar-free water enhancers. All local health aides will be educated about the intervention and the potential for side effects in the case of excess intake and management protocols.

Random samples of sugar-free water enhancers (Tang, Kool-Aid Grape, Kool-Aid Tropical Punch, Kool-Aid Cherry) were obtained to evaluate the concentrations of the 2 artificial sweeteners (sucratose and ace-K). When mixed according to instructions, each 8oz serving contains an average of 43mg of sucratose and 15 mg of ace-K (Tang contains no ace-K). Testing among study staff was conducted to identify the possibility of diluting the drinks with water to increase the maximum volume that could be consumed by study participants. Tables were created that the CHW will use with caregivers to show the maximum amount of sugar-free fruit drink children can consume each day (see Manual of Procedures). Pilot families in the YK Delta tried the diluted recipes and these were well accepted by children and caregivers.

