At each study visit, a CHW or study staff will ask the caregiver about any side effects experienced from the sugar-free water enhancers and will work with the caregiver to assess severity, source, and remedies. If the symptoms or side effects have persisted for more than 48 hours, the CHW will contact the Research Coordinator and Study PI to report the problem to a local health aide. The medical health aides are individuals who live in the communities and are the front-line primary medical care providers in the study communities. They will be asked to follow up with the family and determine the best course of treatment (e.g., monitor, hydration therapy, other). Between study visits, if a caregiver suspects that their child is experiencing side effects associated with the sugar-free water enhancers, they will be asked to contact the CHW. The CHW will then contact the Research Coordinator and Study PI. The Study PI will work with the caregiver and medical health aide to identify the possible cause of the side effects or the relationship of the adverse events to the study intervention.

Side effects/adverse events will be classified as mild, moderate, or severe (see Manual of Procedures). If the side effects are mild or moderate, the child's sugar-free water enhancer intake will be reduced, and the child's side effects will be monitored over the next 48 hours to see if the symptoms resolve. If symptoms are severe or continue past 48 hours, the caregiver will be asked to stop giving the child the sugar-free drinks and to visit the local health aide. If the child's symptoms resolve, caregivers can elect to continue giving their child the sugar-free drinks under close supervision. If the same

symptoms or side effects return a second time, the child's participation in the intervention will be terminated. The child and caregiver will be encouraged to still be involved in all subsequent data collection visits.

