## **8.3 Adverse Events**

An adverse event is any untoward or unfavorable medical occurrence in a human participant, including any abnormal sign (for example, abnormal physical exam or laboratory finding), symptom, or disease, temporally associated with participation in the research, whether or not considered related to participation in the research.

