## **8.5 Time Period and Frequency for Event Assessment and Follow-Up**

The PI will record all events with start dates occurring any time after informed consent is obtained until 7 (for non-serious AEs) or 30 days (for SAEs) after the last day of study participation. At each study visit, the Community Health Worker or Study Staff will inquire about the occurrence of AE/SAEs since the last visit. Events will be followed for outcome information until resolution or stabilization.

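### The only printed caregiver safety questionnaire screens for stomach symptoms alone, which is narrower than the inquiry that sections 8.1 and 8.5 require at each visit

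*Combined protocol and SAP*

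**What the plan says.** Section 7.1 introduces a side effects and adverse events form, describes its purpose as capturing events that excess intake of the water enhancers could cause, and limits it to intervention families. Appendix J prints the form. The interviewer reads an introduction, "The following questions are regarding any adverse incidents that may have happened since the last time we visited", and then asks the one yes/no screening question, whether "has your child or anyone in your family had or currently have an upset stomach, runny stool, or diarrhea". The next item is "Which of the following did your child have? Select all that apply", with the three stomach symptoms and Other as options, followed by "Please specify what type of side effect your child experienced". The remaining items cover severity, the caregiver's view of cause, what helped, and how the drink was mixed, stored, supervised and limited.

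The body of the protocol is broader. Section 8.1 says: "At each study visit, a CHW or study staff will ask the caregiver about any side effects experienced from the sugar-free water enhancers". Beyond gastrointestinal effects it adds: "Additional side effects may include allergic reactions, changes in insulin sensitivity, alterations in gastrointestinal microbiota, weight gain, and decreased satiety". It also lists data to be recorded for each side effect, including onset date, length of symptoms, care sought and the provider's advice. Section 8.5 says that at each visit "the Community Health Worker or Study Staff will inquire about the occurrence of AE/SAEs since the last visit". Section 8.3 defines an adverse event as any untoward medical occurrence, "whether or not considered related to participation in the research".

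**The concern.** The form is the script that community health workers and study staff will have in hand. A caregiver whose child had hives, or a hospital stay, but no stomach complaint can truthfully answer No to the only screening question. The item offering Other asks which of several symptoms the child had, so it reads as a follow-up to a Yes.

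What is at stake is ascertainment. Section 8.8 convenes a safety review when more than 20% of children have symptoms thought to be associated with the enhancers, and the Study Oversight section has the DSMB assess safety data. Both depend on events being elicited. If non-stomach events are not prompted, their absence from the reports says little about whether they occurred.

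**Working it through.** No figure in the plan needs reproducing. The check compares what the protocol commits staff to ask or record with what the printed form prompts.

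| Commitment | Source | Prompt in Appendix J |
|---|---|---|
| Side effects of the enhancers, without restriction, at each visit | 8.1 | One screening question on three stomach symptoms; Other and free text follow it |
| Five additional named side effects | 8.1 | 0 of 5 listed |
| AEs and SAEs since the last visit | 8.5, with scope set by the 8.3 definition | No item on other illness |
| Six seriousness criteria | 8.4 | 0 of 6 listed; no item on hospital stay |
| Onset date, duration, care sought, advice given | 8.1 | 0 of 4 have a field; severity does |

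**How many of the five matter.** Changes in insulin sensitivity and in gut microbiota are not things a caregiver can report: 5 − 2 = 3 remain. Child weight has a field on the child hair survey (Appendix I): 3 − 1 = 2. Allergic reactions and decreased satiety are therefore the two that a caregiver could report and that no printed form captures.

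**How often the form is used.** Section 6 schedules side-effect collection at every visit from 4 to 14: 14 − 4 + 1 = 11 collections. I rely on section 6 because the Appendix A table is displaced in the available text.

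**Whether other forms close the gap.** Section 8.6 calls for a case report form, and section 8.7.1 describes an unanticipated problem report form and an SAE form. Each records or reports an event already known to staff. None comes with wording for asking the caregiver.

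**Link to the review trigger.** Section 8.8 does not state the denominator. Assuming the 136 planned intervention children, 20% is 0.20 × 136 = 27.2, so the trigger is met at 28 children. A child with only a non-stomach reaction attributed to the enhancers should count toward the 28 but is not prompted for.

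**The case against.** A reader might infer that allergic reactions and serious events are never asked about. The documents do not support that. Sections 8.1 and 8.5 are operative instructions to ask, and Appendix J does not limit them. The form's introduction refers to adverse incidents in general, and Other plus free text can hold any event. Appendix J prints no rule that a No hides the later items, whereas the fruit drink survey (Appendix E) prints such a rule where it applies. The Manual of Procedures, which is not available here, may contain a broader prompt.

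Nor is Appendix J the only safety form, given those described in sections 8.6 and 8.7.1. Section 8.3 is a definition and does not itself require inquiry; the duty to ask lies in 8.1 and 8.5. The data listed in 8.1 are to be entered in the study database by the Research Coordinator, and nothing says the fields must sit on this form.

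It is also tempting to say that a new allergy would go undetected. However, the Quality Control section requires the interventionist to confirm continued eligibility at each visit, and sweetener allergy is an exclusion criterion. Caregivers are asked to call between visits if they suspect side effects, and local health aides are trained to recognise them.

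Finally, one might attach a rate. Zero reports among 136 children would give a one-sided 95% upper bound of 1 − 0.05^(1/136) = 2.2%. With the planned 15% to 25% attrition (about 116 to 102 children) the bound is 2.5% to 2.9%. These figures assume that every child was asked and ignore household clustering. They are hypothetical and do not measure the size of this gap.

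What survives is narrower. The introduction has no answer field, Other follows the stomach question, and reporting between visits depends on the caregiver suspecting the enhancers. No printed question prompts for a rash, a hospital stay or an unrelated illness.

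**Conclusion.** The point holds as a mismatch between the form and the protocol text. The one scripted screening question covers three stomach symptoms, while 8.1 and 8.5 commit staff to ask about side effects and adverse events generally. Of the five additional side effects in 8.1, two are both reportable by a caregiver and captured nowhere in print. None of the six seriousness criteria is prompted, and four data items required by 8.1 have no field on the form.

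The effect on event counts cannot be estimated from the documents. It depends on how far staff go beyond the script, on whether a No hides later items in the electronic form, and on what the Manual of Procedures says. The conclusion is that staff who rely on the form could miss non-gastrointestinal and serious events, not that they will. The documents also do not say that a lack of reports would be taken as evidence of safety. The correction is cheap and worth making.

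**What to change.** Reconcile Appendix J with sections 8.1 and 8.5. Add one item asked of every caregiver regardless of the answer to the stomach question, for example: *Since the last visit, has your child had any rash, hives, swelling, trouble breathing, change in appetite, any other illness or health problem, or any clinic visit or hospital stay?* Show the follow-up fields after a yes to either item. Add fields for onset date, duration, care sought and advice given. If the Manual of Procedures already holds a broader prompt, move it onto the form.

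The cost is about one more minute per visit and a minor amendment. More unrelated background illness will be recorded, with no control comparator because section 7.1 gives the form only to intervention families. The change concerns ascertainment and alters no clinical rule.

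Optionally, summarise change in the child weights recorded on the hair survey by arm, since weight gain is a named side effect and section 13.1 does not use these data. With two communities against one and no randomisation, this should be a descriptive safety table, not a test of a causal effect.
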